Because effects will be dependent on patients taking Huperzine, treatment compliance will be essential in our study. We will measure compliance by asking the subject and/or caretaker to return the medication bottles at the end of the titration and maintenance periods. Any remaining pills will be counted, returned to the pharmacy and documented in the subject's folder, with specific forms. If the subject is still inpatient, we will monitor compliance through the medication administration system. Finally, we do not expect significant adverse effects associated with the use of Huperzine that would lead patients receiving this drug to become non-adherent.

Dropout in the placebo group:

Participants in the placebo group may disproportionately discontinue the study treatment since there will be little or no improvements in cognitive function. Although, this fact could bias the results, we expect that the placebo group will also have a small improvement (due to natural recovery, though smaller than in the active group) and we will conduct an analysis of the data using an intent-to treat population, to protect against disproportionate dropout.

XIII. POTENTIAL BENEFITS

It is possible that subjects participating in this research may benefit from the Huperzine-A given in the trial. Additionally, subjects may benefit from the use of TMS as the data could suggest plasticity changes and encourage clinicians to continue therapy or other interventions. Lastly

subjects may benefit from the close follow-up and enhanced observation of the clinical research team.

XIV. STIPEND

Each subject will receive a total of \$450 paid throughout their study participation. The stipend payment distribution is as follows: Screening \$25, Baseline \$25, Week 6 \$50, Week 12 \$100, Week 13 \$50, Week 24 \$100 and Week 52 \$100.

In addition, travel, parking and/or hotel costs will be reimbursed up to \$200/ subject. Proof of payment of costs will be required for reimbursement.

Plan for Future Studies:

A major goal of this study is to collect data that may be useful to plan future phase II/III trials. In fact, this is one of the major goals of phase II studies that usually test several outcomes as there are no strong data to support a large trial. Therefore, with this study we expect to:

- (1) Determine parameters for sample size calculation such as effect sizes for different endpoints.

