Recovery of function after TBI can also be divided into three stages. During the initial phase, activation of cell repair is the main compensation mechanism, leading to resolution of edema and inflammation. This stage takes place mainly over the first three weeks after the injury. The second stage is characterized by substantial changes in previously existing neuronal networks that are reflected both in functional and anatomical cell plasticity leading to the formation of new connections. Plasticity and remyelination are the most important mechanisms governing the final stage of recovery and are usually most prominent within the first three months after the insult. Therefore, it is clear that most changes and recovery occur in the subacute and chronic stages, which share a common underlying physiologic pathway [23, 24].

It is clear that neuroplasticity plays a crucial role in promoting recovery after brain injury, and it can be viewed as a mechanism to compensate for the injury and reestablish function. Thus, understanding the functional and dysfunctional aspects of this ongoing process, as well as the main pathophysiologic events occurring after a TBI, is necessary to create optimal therapeutic approaches [23]. Due to the similar mechanisms subacute and chronic stages share for cell reparation and plasticity, strategies that promote reorganization of neural networks should allow for improvement of cognitive and functional deficits for patients in either phase of recovery [24].

The ability to assess both inpatient and outpatient cases will allow for a broader understanding of the effects Huperzine A has across various stages of recovery. Until now, the majority of studies assessing the effect of Huperzine A have been in outpatient settings, although only in mild to moderate TBI [25]. Thus, by evaluating Huperzine A in both an inpatient and outpatient setting we will have a comparative base by which to determine whether functional and cognitive recovery is in fact similar in subacute and chronic patients. Given that Huperzine A has been tested mainly in the outpatient/chronic setting and that the pathophysiology of the subacute and chronic stages

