encompasses similar recovery mechanisms, we expect that benefits will be equally significant in these two populations. Expanding our study to outpatient population will also have clear benefits on enrollment, given that it will allow us to recruit TBI patients who did not receive direct care from our institution that would potentially otherwise be eligible.

III. OVERALL GOALS

We plan to conduct a phase II, 52 week, randomized, double-blind, placebo-controlled clinical trial that investigates the effect of Huperzine A on memory function in subjects who sustain moderate to severe traumatic brain injury. We will also explore the effects of Huperzine on transcranial magnetic stimulation (TMS)-induced neurophysiologic markers, EEG event related potentials (P50 and P300), seizure frequency/prevalence and incidence of adverse effects as secondary aims. Measures of mood, pain and subjective complaints of concussive symptoms, and length of time post-injury, will serve as covariates to address potential treatment confounders. The data generated from this study will be used to plan a subsequent phase II/III trial with Huperzine A.

IV. SPECIFIC AIMS

Primary Aim:

• To determine whether Huperzine A, as compared to placebo, has a differential effect on learning and memory functions after moderate to severe TBI. We hypothesize that the changes in mean scores on tests of learning and free recall as measured by the California Verbal Learning Test-II (CVLT-II) will be significantly greater after 12 weeks of treatment with Huperzine A in individuals with moderate to severe traumatic brain injury relative to those treated with placebo.

Secondary Aims:

- To determine whether administration of Huperzine A produces significant differences in neurophysiologic markers (as indexed by EEG event related potentials (P50 and P300) and TMS-indexed cortical excitability (cholinergic activity)) associated with cognition relative to a placebo. We expect that patients who receive Huperzine, as compared to placebo, will have decreased latency and increased amplitude for P50 and P300 and, in addition, they will have increased short latency afferent inhibition (as indexed by TMS measurement), thus indicating increased cholinergic activity and cognitive processing at 12 weeks post-enrollment.

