If, in the opinion of the clinical staff or research team, a participant who was originally enrolled in the study by an authorized representative subsequently regains decision-making capacity (e.g., emerges from post-traumatic amnesia), he or she will be re-consented to determine the participant's preference for continued study participation.

During the consent process, participants/authorized representatives will be asked if they would like to be contacted regarding future research opportunities. If the participant/authorized representative chooses not to decide either "yes" or "no" to contact for future research at the time of signing, the co-investigator/coordinator will ask at subsequent follow-up visits, and their pending decision will be tracked. Completion of the study before obtaining an answer will result in that participant not being contacted regarding future research opportunities.

Screening and Baseline Assessments:

As part of the screening process, we will complete the following assessments:

- Neuropsychological examination (i.e., GOAT, Trails B)
- Learning and Memory short form of the Traumatic Brain Injury Quality of Life (TBI-QOL)
- Ruff Neurobehavioral Inventory (RNBI) Postmorbid Cognitive Domain
- Required lab studies (pregnancy test via serum hCG, hepatic, hematologic, and renal function) and physical examination (including vital signs and EKG to rule out cardiac arrhythmias)
- A medical history including seizure history will be obtained via the patient's medical records
- Baseline symptom checklist
- TMS screening checklist

If all eligibility criteria are met and the patient is enrolled in the study, randomization will take place. We will employ a computer-generated randomization scheme to determine whether the subject receives placebo or Huperzine A. Randomization will be performed in permuted blocks of four or eight with random variation of the blocking number to prevent potential unblinding. The randomization code will be kept by a third party with no access to subjects or study data.

Within 7 days of randomization, the following additional baseline assessments will be completed:

- Neurophysiological baseline measures (i.e. P50, P300 and SAI)
- Neuropsychological baseline measures (i.e. CVLT-II,)
- Learning and Memory short form of the Traumatic Brain Injury Quality of Life (TBI-QOL)

- Ruff Neurobehavioral Inventory (RNBI) Postmorbid Cognitive Domain
- Beck Depression Inventory
- Modified Brief Pain Inventory

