Variability in cognitive performance within and across assessments is common in both healthy and neurologically-impaired populations and may exceed two standard deviations in some cases. Practice effects are also common and generally attributable to increased familiarity with test materials, content, and process. To help mitigate these potential influences on test scores, Reliable Change Indices (RCI) [26] will be calculated at the 3 and 12 month reassessments. RCI's are determined by first subtracting the mean T2 - T1 change from the difference between the two testings for each individual, and then comparing it to 1.64 times the standard deviation of the difference. A difference of this magnitude is exceeded only 10% of the time (in either the positive or negative direction) if there is no real change. Applying a correction to change scores is particularly important in samples that include patients with severe TBI, as practice effects are magnified at higher levels of impairment and with shorter test-retest intervals [27].

All subjects will also undergo a neurophysiologic examination at the time of their baseline cognitive testing, and at 6 weeks, 12 weeks, 24 weeks and 52 weeks.

To control for the potential confounding effects of mood, pain and subjective distress on treatment, we will administer self-report measures in these areas at the time of enrollment. Scores on the Beck Depression Inventory, modified Brief Pain Inventory and British Columbia Post-Concussion Scale, obtained at baseline, will be used as covariates in our primary analysis. We will also use time post-injury as a covariate to control for the possible influence of length of time since injury on treatment outcome as spontaneous recovery will be more rapid in subjects enrolled early versus late, and because those enrolled later will be higher functioning at baseline.

Screening/Follow-up measures:

- Galveston Orientation Amnesia Test (GOAT): A series of 10 questions asked to a patient to help evaluate posttraumatic amnesia. The test is repeated at each visit, and is scored on a scale of 0 to 100. A patient is determined to be out of the amnesic state when the score exceeds 75 on three consecutive examinations.

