In designing this exploratory study, we conducted a sensitivity analysis to obtain a sample size that would provide a reasonable effect size when comparing Huperzine A to placebo (Figure 2). This allows for detection of differences between the two treatments, to plan for further studies. Assuming a power of 80% and an alpha of 5%, we originally projected that a sample of 60 patients (30 patients in each group) would allow us to detect an effect size of 0.75 between the two groups (placebo and active). Given our prior studies in TBI and cognition, an effect size of 0.75 for the primary outcome measure (CVLT-II) is clinically meaningful, to compare two treatments.

The authorized addition of two self-report measures to our outcome assessment battery (i.e., Cognitive Function subscale from the Neurological Quality of Life Questionnaire and the Ruff Neurobehavioral Inventory) was expected to influence our original power estimate and required sample size. We calculated our effect size by estimating the upper and lower limits of the change score that would be demonstrated by the control group on our primary outcome measure (i.e., California Verbal Learning Test-II). This analysis showed that, to achieve an effect size of 0.75, the final sample size could vary between 15 and 39 subjects per group, given a mean difference

in performance between groups of 3.59 with a standard deviation of 3.30 to 5.13. In view of the variability in this estimate, we proposed that we would run 10 subjects, determine the degree of variability in performance and then adjust the sample size accordingly.

After enrolling 10 subjects, we assessed the data for an estimate of the average difference between groups (difference to baseline) on a ratio of 3:6. There was an estimated effect size of 1.19 between group A (M=4.67, SD=4.51) and group B (M=0.33, SD=2.50). Using a two sample t-test to detect the difference between groups, a minimum sample of 26 subjects will be required (13 per group).

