The anticipated loss to follow-up rate in this study is around 15% - like our other drug studies. To account for this loss-to-follow-up rate, a total of 15 patients per group (30 total) will be enrolled in the study. The primary analysis will be an intent-to-treat analysis that will include all randomized participants regardless of their compliance with the study treatment or follow-up schedule. Study subjects should have received at least 1 dose of study drug/placebo. All hypothesis testing will be conducted using $\alpha = 0.05$, two-sided.

To analyze the data, we will compare means using t-test and modeling the data with ANOVA for multivariate analysis controlling for baseline values and other important covariates. If necessary, non-parametric approaches including Mann-Whitney and Friedman's test for multivariate analysis will be used with data that are not normally distributed. We will also use Fisher's exact test for comparison of categorical variables such as proportion of adverse effects. In summary, we will use the following statistical tests according to our primary aims:

• Primary Aim: To determine whether Huperzine A, as compared with placebo, has a differential effect on learning and memory functions after moderate to severe TBI.

For this aim we will compare means using t-test (comparing differences (Week 12 – baseline) between the two groups) and modeling the data with ANOVA for multivariate analysis controlling for baseline values and other important covariates (for secondary analysis). If necessary, non-parametric approaches including Mann-Whitney and Friedman's test for multivariate analysis will be used with data that are not normally distributed.

• Secondary aim 1: To determine whether administration of Huperzine A produces significant differences in neurophysiologic markers (as indexed by EEG event related potentials (P50 and P300) and TMS-indexed cortical excitability (cholinergic activity)) associated with cognition, relative to a placebo.

For this aim we will also build models in which the main dependent outcome will be amplitude or latency measures (from P50, P300 and SAI) and the independent variables will be group, time and the interaction group*time.

• Secondary aim 2: To determine whether Huperzine A reduces the prevalence of post-traumatic seizures after moderate and severe TBI as compared to placebo

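### Section II promises to settle whether recovery is similar in subacute and chronic patients, but the plan has no stage definition, no stage analysis and too few subjects to do so

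*Combined protocol and SAP*

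**What the plan says.** Section II (Rationale for Expanding the Study to Include Outpatients) says that with both settings in the trial "we will have a comparative base by which to determine whether functional and cognitive recovery is in fact similar in subacute and chronic patients". It then states the expected answer: "we expect that benefits will be equally significant in these two populations". The section pairs inpatients with the subacute stage and outpatients with the chronic stage. Section VI sets a maximum of one year since injury for everyone, no minimum for outpatients, and no point at which subacute becomes chronic.

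The comparison is not among the primary or secondary aims in Section IV. Section X contains no treatment-by-stage term for the CVLT-II, no subgroup estimate, no similarity margin and no sample size for the question. Under Screening and Baseline Assessments, Section VIII says: "Randomization will be performed in permuted blocks of four or eight with random variation of the blocking number to prevent potential unblinding". It names no stratification factor.

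The plan does treat stage as prognostic. Section IX (Outcome measures) says that "spontaneous recovery will be more rapid in subjects enrolled early versus late", and for that reason makes time post-injury a covariate, as do Section III and the Covariates list in Section IX. The place of that covariate is unclear. Section IX attaches the mood, pain and symptom covariates to the primary analysis and adds time post-injury in the next sentence. Section X, under the primary aim, makes an unadjusted t-test on Week 12 change the main comparison and assigns the covariate model to secondary analysis.

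**The concern.** Section II claims a property that the design does not have. To conclude that two stages respond similarly, one needs a definition of the stages, a contrast, a margin, and an interval narrow enough to fall inside that margin. None of these is planned. Without them, similar can only mean not significantly different, and in about 26 subjects that result is likely even if the stages respond quite differently. Because Section II already expects equal benefit, a null subgroup finding could be carried into the planned phase II/III trial as support for pooling stages.

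Using setting as a proxy adds misclassification. An outpatient two months after injury would count as chronic, and an inpatient at six months as subacute.

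The second issue is the main contrast. If Section X governs, the headline result is not adjusted for a factor that the plan itself says drives spontaneous recovery, and in a trial of 30 the arms can differ noticeably on it by chance.

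**Working it through.** **The plan's own sample size.** Section X reports: "There was an estimated effect size of 1.19 between group A (M=4.67, SD=4.51) and group B (M=0.33, SD=2.50"). The difference is 4.67 − 0.33 = 4.34 points, and the root-mean-square SD is √((4.51² + 2.50²)/2) = 3.65. So d = 4.34/3.65 = 1.19, as stated. At two-sided α = 0.05 and 80% power (stated for the original plan and assumed to carry over), the noncentral t gives 12.12 per arm, rounded up to 13, or 26 in total, with 82.9% power. Then 26 × 1.15 = 29.9, or 30 enrolled. The plan's figures reproduce, and they size only the drug–placebo comparison.

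**Difference in treatment effect between stages.** Assumptions: a common SD for Week 12 change and an equal arm split within each stage. The documents give no stage mix, so 50:50 is taken as the best case. With n₁ and n₂ subjects per arm in the two stages, SE = SD × √(2/n₁ + 2/n₂), with N − 4 degrees of freedom.

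For 26 evaluable and a 50:50 mix, n₁ = n₂ = 6.5:
- SE = √(4/6.5) = 0.784 SD
- t(0.975, 22 df) = 2.074
- 95% half-width = 2.074 × 0.784 = 1.63 SD, or about 5.9 points at SD 3.65

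Section X says that "an effect size of 0.75 for the primary outcome measure (CVLT-II) is clinically meaningful". The half-width is 1.63/0.75 = 2.2 times that figure.

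| Evaluable | Stage mix | 95% half-width (SD) | Power, 0.75 SD | Power, 1.19 SD |
|---|---|---|---|---|
| 26 | 50:50 | 1.63 | 15% | 31% |
| 26 | 30:70 | 1.78 | 13% | 26% |
| 30 | 50:50 | 1.50 | 17% | 35% |
| 30 | 20:80 | 1.88 | 12% | 24% |

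With 26 evaluable and a 50:50 mix, the smallest stage difference detectable with 80% power is 2.3 SD.

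**Showing similarity.** The documents give no margin, so 0.75 and 1.19 SD are assumed to show a range. The method is two one-sided tests at 5% each, with a true difference of zero.
- Treatment effects alike across stages, 26 evaluable: power is about 3% at a margin of 1.19 SD and about 0% at 0.75 SD.
- Overall recovery alike across stages, arms pooled, 26 evaluable: power is 81% at 1.19 SD and 19% at 0.75 SD. With 30 evaluable it is 88% and 29%.

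**Size needed for 80% power** (normal approximation, four equal cells):
- To detect a stage difference m, n per cell = 4(1.960 + 0.842)²/m². This gives 23 per cell (92 in total) at 1.19 SD and 56 per cell (224) at 0.75 SD.
- To show equivalence within m, n per cell = 4(1.645 + 1.282)²/m². This gives 25 per cell (100) at 1.19 SD and 61 per cell (244) at 0.75 SD.

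**Chance imbalance in stage.** Permuted blocks of 4 or 8, chosen at random and cut at 30 subjects, were simulated. The arms differ by 20 percentage points or more in the share of early subjects in about 32% of trials if each subject has a 50% chance of being early, and in about 39% if exactly 15 of the 30 are early. If the stages differed by 1 SD in 12-week change (an assumption), a 20-point imbalance would move the unadjusted treatment difference by 0.20 × 1 SD = 0.2 SD, or 0.20 × 3.65 = 0.7 points, against the design difference of 4.34.

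**The case against.** The sentence in Section II is rationale for wider recruitment, which the section also justifies by enrolment. It is not an aim, Section X calls the study exploratory, and no stage test is planned. All of that stands. A reader might infer that the trial fails one of its objectives; Section IV does not support that. What remains is a claim to determine something that the data cannot determine.

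A reader might also infer that the main contrast is unprotected against stage, or biased by it. The documents do not support that either. Time post-injury is a planned covariate in Sections III and IX. Imbalance under valid randomization is chance, which the test's error rate already allows for. It can distort one small trial's estimate but is not systematic bias. The defect is narrower: Sections IX and X place the adjustment in different analyses.

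Nor does Section II set three months as the line between subacute and chronic. It says that certain recovery mechanisms are most prominent within that period. And Section IX lists practice effects, mood, pain, distress and time post-injury without ranking them, so stage cannot be called the strongest influence.

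Stratification might look like the natural remedy. Ten subjects had been enrolled when the sample size was revised, so at most 20 of 30 could be stratified. Changing the allocation scheme mid-trial has a cost, and smaller blocks at a single site would make assignments easier to guess. It would not make the similarity question answerable.

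**Conclusion.** The concern holds in limited form. Section II says that the trial will determine whether recovery is similar across stages, while the plan gives no stage definition, contrast or margin. In the best case the interval for the difference in treatment effect is ±1.63 SD with 26 evaluable (±1.50 SD with 30), about twice the effect that the plan calls meaningful. Uneven stage mixes make it wider. Read as overall recovery with the arms pooled, similarity could be shown with reasonable power only within a margin near 1.19 SD, not within 0.75 SD.

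These figures rest on a common SD and on assumed stage mixes and margins, since the documents give none. The 0.7-point shift also rests on an assumed 1 SD gap between stages.

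The drug–placebo comparison is not invalidated. Its exposure to chance stage imbalance depends on whether Section IX or Section X governs the covariates, and the two must be reconciled.

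**What to change.** 1. Define stage by time since injury rather than care setting, with a cut-off that the sponsor fixes before unblinding. Three months is one option.
2. In Section II, replace the promise to determine similarity with a descriptive estimate of the treatment difference in Week 12 CVLT-II change within each stage, and of the difference between stages, each with a 95% confidence interval. State that no claim of similarity or equal benefit will be made from these. Add the matching sentence to Section X.
3. Reconcile Sections IX and X so that adjustment for time since injury is explicit in the primary analysis. This handles chance stage imbalance for all 30 subjects, including those already enrolled. A linear term may leave some imbalance uncorrected if recovery is not linear in time, so the form of the term should be stated in advance.

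Stratifying the remaining randomizations by time since injury is optional. The cost is a few sentences and one degree of freedom for a linear term in the primary model. No patients, visits or assessments are added.

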- To determine whether Huperzine A reduces the prevalence/frequency of post-traumatic seizures after moderate and severe TBI as compared to placebo. We hypothesize that the prevalence of seizure will be significantly lower at 12 weeks post-enrollment (immediate seizures prevalence) in subjects treated with Huperzine A relative to those treated with placebo.
- To evaluate the safety and tolerability of Huperzine A in this patient population as compared to placebo. Safety and tolerability will be assessed by a comparison of the frequency and intensity of adverse effects. We hypothesize that the incidence of clinically significant adverse effects will be no different in subjects treated with Huperzine A relative to those treated with placebo.

V. INVESTIGATORS

[name], DO Spaulding Rehabilitation Hospital

Principal Investigator

[name], PhD Spaulding Rehabilitation Hospital

Co-Investigator, recruitment, screening and consenting, data collection and analysis

[name] Spaulding Rehabilitation Hospital

Co-Investigator, recruitment, screening and consenting, cognitive assessment, outcome measurement and analysis

[name] Spaulding Rehabilitation Hospital

Research Nurse Coordinator

[name] Spaulding Rehabilitation Hospital

Co-Investigator- Study physician

[name] Spaulding Rehabilitation Hospital

Co-Investigator-Study physician

VI. SUBJECT SELECTION

We plan to enroll 30 subjects with moderate to severe TBI (Huperzine = 15, Placebo = 15).

Inclusion criteria:

- Males and females aged 18 to 65
- Meeting at least one of the following criteria for moderate or severe TBI:
 - PTA > 24 hours
 - Trauma related intracranial neuroimaging abnormalities
 - Loss of consciousness exceeding 30 minutes (unless due to sedation or intoxication)
 - GCS in the emergency department or ICU of less than 13 (unless due to intubation, sedation, or intoxication). If there is no GCS score available from the ED or ICU, the GCS from the scene can be documented.

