Changes in pupil diameter due a cognitive task are considered a reliable and sensitive index of the degree of cognitive load and resource demand to the task. We will record pupillary response, indexed as changes in pupil diameter, to two sets of tasks measuring cognitive performance: a low cognitive-load task vs. a high-cognitive load task. The first will consist of a set of simple stimuli presented to the patient in an organized and timely manner, which will then be recognized and named by the subject. The high-cognitive load task includes the presentation of a larger and more complex array of information for the subject to recall. Both sets of stimuli will be shown in a computer screen with a fixed interval between stimuli. Measurement of pupil diameter and reactivity will be conducted with a remote eye-tracker device. It consists of a high-resolution 17" computer screen placed in front of the subject's face that allows both stimuli display and pupil tracking through infrared diodes that generate reflection patterns of the user's cornea.

• Smooth pursuit eye movement (SPEM):

Eye movements will be recorded by an infrared-based eye-tracking device consisting of a high-resolution computer screen that will be placed in front of the subject's face at a 40cm distance. Subjects will be presented with a target stimulus that will move in a predetermined and consistent trajectory in the fixed background screen. We will measure different parameters based on this recording both at baseline and treatment completion, including eye and target velocity, index of target prediction, eye position error and intraindividual variability of eye error. Comparison of baseline to after-treatment measurements will be considered a reflection of cognitive changes.

X. STATISTICAL ANALYSIS

This is an exploratory phase II study with the intent of generating hypotheses for a confirmatory phase II/III trial, as well as in obtaining effect sizes and variances for sample size calculation for further confirmatory studies. The study is also designed to address the tolerability of Huperzine A in the moderate and severe TBI populations.

[figure not shown]

Figure 2: Effect size to total sample size ratio necessary for a powerful study

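### The safety aim predicts no difference in adverse effects, but the only test named for it (Fisher's exact test, 15 per arm, no margin or interval) cannot support that prediction

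*Combined protocol and SAP*

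**What the plan says.** Section IV (Specific Aims, Secondary Aims) states the safety hypothesis: "the incidence of clinically significant adverse effects will be no different in subjects treated with Huperzine A relative to those treated with placebo". The same bullet says how it will be judged: "Safety and tolerability will be assessed by a comparison of the frequency and intensity of adverse effects".

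Section X (Statistical Analysis) describes the trial as exploratory but adds: "The study is also designed to address the tolerability of Huperzine A in the moderate and severe TBI populations". Its general text names the test: "We will also use Fisher's exact test for comparison of categorical variables such as proportion of adverse effects". All hypothesis tests are two-sided at 0.05. The entry for secondary aim 3 in section X mentions only the frequency of adverse effects and laboratory abnormalities. It names no test, and no method is given anywhere for intensity.

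The arm size of 15 comes from the CVLT-II calculation in section X. For safety there is no equivalence or non-inferiority margin, confidence interval, assumed rate or power.

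**The concern.** The stated hypothesis is the null hypothesis of the only test named. A difference test can count against a null hypothesis but cannot establish it, and failing to reject is weak evidence when the test has little power. As planned, the one test result consistent with the hypothesis is also the likely result when the drug moderately raises adverse-effect rates.

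At stake is the tolerability statement at the end of the trial. Tolerability is a declared purpose of the study, and section III (Overall Goals) says the data will be used to plan a later phase II/III trial. A report of no significant difference, without an interval, could carry more reassurance into that trial than 30 patients can provide.

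**Working it through.** **1. Where 15 per arm comes from.** Inputs from section X: group changes 4.67 (SD 4.51) and 0.33 (SD 2.50).

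d = (4.67 - 0.33) / sqrt((4.51² + 2.50²)/2) = 4.34 / 3.646 = 1.19.

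A two-sided two-sample t-test at 0.05 with 80% power needs 12.12, so 13 per group (power 82.9%), which matches the plan's 26. For 15% loss, 26 × 1.15 = 29.9, giving the plan's 30; 26/0.85 = 30.6 would give 31. The figure reproduces, within one patient, and rests on CVLT-II alone.

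**2. Power of the safety comparison.** With n = 15 per arm, power is the sum over all counts x (active) and y (placebo) of Bin(x; 15, pA) × Bin(y; 15, pP), taken where the two-sided Fisher p ≤ 0.05. All rates below are assumptions.

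| Placebo | Active +20 points | Active +30 points | Active +40 points |
|---|---|---|---|
| 0% | 16% | 49% | 78% |
| 10% | 15% | 33% | 54% |
| 20% | 11% | 25% | 45% |
| 30% | 10% | 23% | 43% |

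From placebo rates of 0%, 10% and 20%, a true 20-point excess is missed 84%, 85% and 89% of the time. For 80% power the active rate must reach about 41%, 64%, 76% or 86% when the placebo rate is 0%, 10%, 20% or 30%. With 13 per arm, power for 10% versus 30% falls to 12%. The test is also conservative: its actual type I error is 0.5% to 1.7% at common rates of 10% to 40%.

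**3. Results that stay non-significant.**
- 4/15 versus 0/15: p = 2 × C(15,4)/C(30,4) = 2 × 1365/27405 = 0.10.
- 5/15 versus 0/15: p = 2 × 3003/142506 = 0.042, the smallest significant result when placebo has no events.
- 6/15 versus 1/15: p = 0.08.
- 8/15 versus 2/15: p = 0.0502.

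**4. What an interval would show.**
- 3/15 versus 3/15: the Wilson limits for each arm are 7.05% and 45.19%. The Newcombe limits for the difference are ± sqrt((0.200 - 0.0705)² + (0.4519 - 0.200)²) = ±0.283, so -28 to +28 points.
- 1/15 versus 1/15: -24 to +24 points.
- 0/15 in one arm: the exact two-sided 95% upper limit is 1 - 0.025^(1/15) = 21.8%.
- 6/15 versus 1/15: Newcombe interval about +3 to +58 points, where Fisher's test alone says not significant.

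**5. What a formal claim of no worse would need.** With equal true rates p, one-sided 0.025 and 80% power, n per arm = (1.960 + 0.842)² × 2p(1 - p)/m². For an assumed margin m of 10 points this is 142, 252 or 330 per arm at p = 10%, 20% or 30%. Turned round, 15 per arm can exclude only margins of about 31, 41 or 47 points.

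**The case against.** The best defence is that the aim states an expectation and not a decision rule. A reader might infer that the plan makes p > 0.05 its criterion for safety, or that such a result will be misread. No sentence says so. Fisher's test appears in a general sentence, and in the per-aim entries it is assigned explicitly to seizures (secondary aim 2) but not to safety. The plan also intends to compare intensity, and the Drug Side Effects Checklist in section XII grades severity from 1 to 3. This stands: the most the text supports is that non-significance could be taken as support for the hypothesis.

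A second tempting reading is that the test would fail to reject almost whatever the truth. The table contradicts that for very large excesses.

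Third, low safety power is usual in a trial of this size, and the sample was set for CVLT-II. The small number is not in itself an error. Section X calls the study hypothesis-generating, and section XI provides an unblinded DSMB with stopping rules that include a disproportionate incidence of serious adverse events. Patient protection during the trial therefore does not depend on this test. That limits the consequence, but neither the exploratory label nor the DSMB supplies a margin or interval for the final conclusion. An exploratory study meant to yield effect sizes is better served by estimation than by a hypothesis of no difference.

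**Conclusion.** The point holds as one of hypothesis wording and analysis choice. The plan pairs a hypothesis of no difference with a difference test and offers nothing else by which that hypothesis could be supported. Moderate excesses would usually be missed: power is 11% to 16% for 20 points (placebo 0% to 20%) and 25% to 33% for 30 points (placebo 10% to 20%). A 30-point excess over a zero placebo rate would be found about half the time (49%). These figures rest on assumed adverse-effect rates, on 15 evaluable patients per arm and on a two-sided 0.05 Fisher's test. The ±28-point interval and the 22% upper limit need no assumed true rate; they follow from the illustrative counts. The consequence is limited to the closing tolerability statement and the planning of the next trial. The change should be made, but the point does not threaten the primary analysis.

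**What to change.** In section IV, replace the hypothesis of no difference with an estimation aim. In the secondary aim 3 entry of section X, specify per-arm rates and the risk difference (active minus placebo) with a 95% interval for the plan's own endpoint of clinically significant adverse effects, and also for serious adverse events and for stopping study drug because of intolerance. Name one interval method in advance, exact or score-based. A score-based interval can exclude zero when Fisher's p exceeds 0.05, as with 6/15 versus 1/15, so the plan should say that the interval carries the interpretation. Add a sentence that a non-significant Fisher p-value will not be read as evidence of equal safety.

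The cost is a few lines of text, a few interval calculations and a less favourable safety statement. No extra patients are needed.
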